6.1.8. Data Adjustments/Handling/Conventions

All collected data will be presented in Clinical Data Interchange Standards Consortium (CDISC) datasets. Data not subject to analysis according to this plan will not appear in any tables or graphs but will be included only in the CDISC datasets.

All *P* values will be displayed in four decimals and rounded using standard scientific notation (eg, 0.XXXX). If a *P* value less than 0.0001 occurs it will be shown in tables as <0.0001; similarly, if a *P* value greater than 0.9999 occurs it will be shown in tables as >0.9999.

Adverse events will be coded using the MedDRA version 24.1 thesaurus. Medications will be coded using the World Health Organization Drug Dictionary Enhanced (WHO-DDE) Global B3 version September 2021.

A treatment-related AE is any AE with a relationship to the study drug of possibly related, probably related, likely related, or missing.

For partial AE and medication start dates:

- If the year is unknown, then do not impute the date but assign a missing value.
- If the year is known, but the month or month and day is unknown, then:
 - If the year matches the year of first dose date and the end date (if present) is after first dose date, then impute as the month and day of the first dose date.
 - Otherwise, assign 01 January.
- If the year and month are known, but the day is unknown, then:
 - If the month and year match the month and year of the first dose date, then impute as the day of the first dose date.
 - Otherwise, assign 01.

For partial AE and medication end dates:

- If the year is unknown, then do not impute the date but assign as missing value.
- If the year is known, but the month or month and day is unknown, then:
 - If the year matches the year of the last date of the study (date of last contact if subject lost to follow-up; date of completion or early termination otherwise), then impute as the month and day of the last date of the study.
 - Otherwise, assign 31 December.
- If the year and month are known, but the day is unknown, then:
 - If the month and year match the month and year of the last date of the study, then impute as the day of the last date of the study.
 - Otherwise, assign the last day of the month.

6.2. Special Handling for COVID-19 Disruptions

The impact of COVID-19 on this clinical trial and participants will be assessed by including in summaries/listings relevant information as captured on the eCRF. Information collected will include the following:

- Any visit disruption caused by COVID-19
- Early termination due to COVID-19
- Weight loss due to complications associated with COVID-19
- Local tolerability assessment and WI-NRS disruption caused by COVID-19
- Study drug interruption (missed dose) due to COVID-19
- Delay in any assessment caused by COVID-19
- Protocol deviation due to COVID-19

7. Study Subjects and Demographics

The disposition, demographics and baseline characteristics, medical/surgical history, prior/concomitant medication, protocol deviations, and exposure will be summarized as indicated below in two separate tables for the associated baseline type defined in section 6.1.1:

Cohort 1 Group 1 (ARQ-154-203 roflumilast foam 0.3%, ARQ-154-203 vehicle, and total for subjects that consented to rollover into this extension study without gap),

Cohort 2 Group 3 (ARQ-154-203 roflumilast foam 0.3%, ARQ-154-203 vehicle, and total for subjects that enrolled into this study with a gap),

Cohort 2 Group 4 (de novo subjects),

Cohort 2 Total, and

Overall (includes all the cohorts and groups listed above).

Due to few number of subjects rolling over from study ARQ-154-116 (Cohort 1 Group 2), information collected from ARQ-154-116 will only be included in the listings.

7.1. Subject Disposition

Disposition summary will include tabulation of the number of subjects who enrolled into each cohort/group, the number of subjects who received treatment, number of subjects who completed the study, number of subjects who prematurely discontinued the study, the reasons for

discontinuation from the study overall and due to COVID-19 disruption, and number of subjects in each analysis population as identified in Section 5.

7.2. Demographics and Baseline Characteristics

Summary statistics for age, age groups (9-11 years old, 12-17 years old, 18-64 years old, and ≥ 65 years old), gender (including child-bearing potential), ethnicity, race, height, weight, baseline disease characteristics (IGA, Overall Assessment of Erythema, Overall Assessment of Scaling, Scalpdex total score, WI-NRS, percent BSA [total]), and BMI will be presented.

A summary of treatment history, including history of response, intolerance, or contraindication to topical corticosteroids and/or topical antifungals, and subjects having facial involvement and current scalp involvement will be provided.

For the continuous variables, the number of non-missing values and the mean, SD, minimum, Q1, Q3, median, and maximum will be tabulated.

For the categorical variables, the counts and proportions of each value will be tabulated.

For ordinal variables such as the IGA, Overall Assessment of Erythema, Overall Assessment of Scaling, and WI-NRS, summary statistics including the mean, median, Q1, Q3, and range of the ordinal variable will be presented as well as frequency counts of each level of the ordinal variable.

These analyses will be conducted for the Safety population. Baseline characteristics will be presented for both primary and OLE baselines.

7.3. Prior and Concomitant Medications

Prior and concomitant medications will be summarized descriptively by Anatomical Therapeutic Chemical (ATC) level 4, and preferred term using counts and percentages for Safety population.

Prior medications will be presented separately from concomitant medications. Medications that started before the first application of IP will be considered prior medications whether or not they were stopped prior to the first application of IP. Any medications continuing or starting after the first application of study drug will be considered to be concomitant. If a medication starts before the first application of study drug and continues after the first application of study drug it will be considered both prior and concomitant. This will include only medications that started after the first dose of IP in this extension study (ARQ-154-214).

Medications will be coded using WHODrug Global B3, version September 2021.

7.4. Surgical and Medical History

Surgical and medical history will be coded according to the MedDRA, Version 24.1.

Surgical and medical history will be summarized by system organ class (SOC) and preferred term (PT) using the Safety population. A subject who experienced the same surgical and medical history event multiple times will be counted only once for the corresponding PT. Similarly, if a subject experienced multiple surgical and medical history events within the same SOC, the subject will be counted only once for that SOC. Surgical and medical history events will be sorted alphabetically by SOC and within each SOC, the PT will be presented by descending order.

7.5. Protocol Deviations

A data review will be conducted before database lock by the Medical Monitor and the Sponsor to identify protocol deviations as important or non-important.

The number of subjects with important protocol deviations and/or eligibility deviations in this study will be summarized, including protocol deviations that are related to COVID-19 disruptions and COVID-19 infections for the subjects in Safety population by groups and overall.

All of the protocol deviations (including important or non-important protocol deviations) will be provided in the data listings.

7.6. Exposure and Compliance

The number of IP applications by each subject based on diary data will be summarized using descriptive statistics appropriate for continuous variables.

The amount of IP used by each subject based on can weight will be summarized descriptively using continuous methods.

The number of days on IP will be derived as indicated in Section [6.1.7](#) and summarized descriptively.

The gap between completing study ARQ-151-203 and enrolling into this study will not be included in the above definition and will be summarized separately for subjects in Cohort 2 Group 3.

A subject will be considered compliant with the dosing regimen if the subject applies at least 80% of the expected applications during the IP application period and does not miss more than 3 consecutive doses. Doses missed due to IGA clearance were not considered as noncompliance.

AD-ST-33.06 Effective date: 12-Nov-2020

The number and percent of subjects that missed more than 3 consecutive doses will be tabulated except for subjects who withheld IP application due to IGA clear per investigator.

Investigational product application compliance will be calculated based on number of applications divided by the expected number of IP applications. Compliance will be summarized descriptively using the following categories:

- > 100%
- $\geq 80\% - \leq 100\%$
- < 80%

Drug exposure and compliance will be presented using primary and OLE baselines. The number of subjects with treatment duration (≥ 1 day, ≥ 8 weeks, ≥ 12 weeks, ≥ 24 weeks, ≥ 32 weeks, ≥ 54 weeks, and ≥ 62 weeks) will also be summarized similarly. Study duration will be summarized from primary and OLE baseline.

Similar exposure and compliance information will be summarized for subjects who completed or discontinued study before protocol amendment 1.

8. Efficacy Analysis

This study is open label without a comparator group; therefore, there will be no formal hypothesis testing performed in the study.

For the continuous variables, the number of nonmissing values and the mean, SD, minimum, Q1, Q3, median, and maximum will be tabulated by study visit; similarly, categorical variables will have the counts and proportions of each value will be tabulated by study visit.

For efficacy summaries 2 baselines will be used (primary and OLE) using Safety population as defined in Section [6.1.1](#).

All efficacy summaries for primary and OLE baselines will be presented as indicated below:

Cohort 1 Group 1 (ARQ-154-203 roflumilast foam 0.3%, ARQ-154-203 vehicle, and total for subjects that consented to rollover into this extension study without gap),

Cohort 2 Group 3 (ARQ-154-203 roflumilast foam 0.3%, ARQ-154-203 vehicle, and total that enrolled into this study with a gap),

Cohort 2 Group 4 (de novo subjects),

Cohort 2 Total, and

Overall (includes all Cohorts and groups).

For vehicle subjects in Cohort 1 Group 1, Cohort 2 Group 3, de nova subjects in Group 4, primary baseline is the same as OLE baseline.

Due to the few number of subjects rolling over from the study ARQ-154-116, information collected from ARQ-154-116 will be included in the listings only.

Missing data for efficacy variables will not be imputed.

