4.1. Introduction

Data processing, tabulation of descriptive statistics, calculation of inferential statistics, and graphical representations will primarily use SAS® (release 9.4 or higher). If the use of other software is warranted, the final statistical methodology report will detail what software was used for what purposes.

Continuous (quantitative) variable summaries will include the number of subjects (n) with non-missing values, mean, standard deviation (SD), median, Q1, Q3, minimum, and maximum.

Categorical (qualitative) variable summaries will include the frequency and percentage of subjects who are in the particular category or each possible value. In general, the denominator for the percentage calculation will be based upon the total number of subjects in the study population for the treatment group unless otherwise specified. The denominator for by-visit displays will be the number of subjects in the relevant study population with non-missing data at each visit.

The minimum and maximum will be reported with the same degree of precision (i.e., the same number of decimal places) as the observed data. Measures of location (mean, median, Q1, and Q3) will be reported to 1 degree of precision more than the observed data and measures of spread (SD) will be reported to 2 degrees of precision more than the observed data, unless otherwise specified or modified upon request of the sponsor.

Percentages will be presented to 1 decimal place, unless otherwise specified.

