6.1.4. Analysis Visit Windows

Visits will be analyzed as scheduled. Unscheduled, early termination visits, and/or repeated measurements will only be included if a scheduled measurement is not available and the early termination or unscheduled/repeated measurement falls within the analysis visit windows as described in [Table 2](#) and [Table 3](#). The windows follow the Schedule of Events in [Table 1](#). For subjects in Cohort 2 Group 3, the gap between completion of parent study and starting of the study ARQ-154-214 should not be counted in the analysis visit window. The windowing will be applied using the days on study as shown in the [Table 2](#). Unscheduled/repeated measurements will be listed.

Table 2: Analysis Visit Windows (Primary Baseline for Cohort 1 Group 1 & Cohort 2 Group 3)

		Primary Baseline for Group 1 - Roflumilast & Group 3 - Roflumilast	
Scheduled Visit	Target Days on Study	Window (Days)	

ARQ-154-203 Week 2	14	2 to 22
ARQ-154-203 Week 4	28	23 to 42
ARQ-154-203 Week 8	56	43 to 61
Week 4 OLE	85	71 to 113
Week 12 OLE	141	114 to 183
Week 24 OLE	225	184 to 267
Week 36 OLE	309	268 to 365
Week 52 OLE	421	≥ 366

Table 3: Analysis Visit Windows

Primary Baseline for Cohort 1 Group 1 - Vehicle & Cohort 2 Group 3 - Vehicle Cohort 2 Group 4 + OLE Baseline for Cohort 1 Group 1 - Roflumilast & Cohort 2 Group 3 – Roflumilast		
Scheduled Visit	Target Study Day	Window (Days)
ARQ-154-203 Week 2	n.a.	n.a.
ARQ-154-203 Week 4	n.a.	n.a.
ARQ-154-203 Week 8	n.a.	n.a.
Week 4 OLE	29	15 to 57
Week 12 OLE	85	58 to 127
Week 24 OLE	169	128 to 211
Week 36 OLE	253	212 to 309
Week 52 OLE	365	≥ 310

n.a. = not applicable

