6.1.7. Derived Variables

- **IGA success** = IGA of “completely clear” or “almost clear” plus a 2-grade improvement from Baseline. For IGA success analysis, the subjects who achieved IGA of 0 or 1 at baseline will be excluded from the analysis.
- **Erythema success** = Erythema score of 0 or 1 plus a 2-grade improvement from Baseline as observed over time. For erythema success analysis, the subjects who achieved erythema score of 0 or 1 at baseline will be excluded from the analysis.
- **Scaling success** = Scaling score of 0 or 1 plus a 2-grade improvement from Baseline as observed over time. For scaling success analysis, the subjects who achieved scaling score of 0 or 1 at baseline will be excluded from the analysis.
- **Compliance** = number of applications divided by the expected number of investigational product (IP) applications for each subject. Compliance will be calculated using drug accountability data over the entire treatment period for each subject, up to treatment completion or discontinuation.
- **Number of expected IP applications** = calculated as last treatment date - first treatment date + 1. Excluding treatment-free interval time (defined in this section).
- **Number of IP applications** = number of expected IP applications – missed IP applications as collected in the CRF. Missed IP applications will not be taken into consideration in determining number of IP applications if the reason for missing dose is per investigator confirmation of clear.

- **Days on IP** = last date of IP application – first date of IP application +1. Subjects that stop taking IP per investigator confirmation of clear will be excluded from this calculation.
- **Treatment Gap** = This will be calculated for subjects belonging to Cohort 2 Group 3 that rolled into the extension study (ARQ-154-214) with a gap. This is derived start treatment start date in ARQ-154-214 – last treatment date in ARQ-154-203 + 1.
- **Treatment Duration (weeks)** = (last date of IP application – first date of IP application +1)/7.
- **Duration of IGA success** = The date of first observation where IGA does not meet success criteria - the date of first observation of IGA success + 1. The duration of IGA success for subjects who end treatment in IGA success will be censored at the last disease assessment date. Only the first duration of IGA success will be analyzed.

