- **Duration of IGA of 0** = the date of first observation of IGA > 0 - the date of first observation of IGA of 0 and stop treatment. The duration of IGA of 0 for subjects who end treatment in IGA success will be censored at the last disease assessment date. This is for subjects who achieve IGA of 0 and stop the treatment. Subjects who achieve IGA of 0 but never stop treatment will be excluded from the analysis. For subjects who achieve IGA of 0 but stop the treatment later, the duration starts from the date of stop treatment. Only the first IGA of 0 duration will be analyzed.
- **Duration of IGA of 0 or 1** = the date of first observation of IGA > 1-the date of first observation of IGA of 0 or 1 + 1. The duration of IGA of 0 or 1 for subjects who end treatment in IGA of 0 or 1 will be censored at the last disease assessment date. Only the first IGA of 0 or 1 duration will be analyzed.
- **Disease recurrence** = the date of first observation of IGA of 2 or above after achieving IGA of 0 and stop treatment - the date of first observation of IGA of 0 + 1. Only the first disease recurrence will be analyzed.
- **Treatment-free interval** = the date of re-starting study drug due to IGA score above 0 - the date of stop treatment due to attainment of score of IGA of 0 +1, among subjects who achieve a “completely clear” IGA and stop treatment to all lesions. If subjects never re-start study drug after stopping treatment, the treatment-free interval is censored at the end of study date. Only the first treatment-free interval will be analyzed.
- **Weight of IP (g)** = dispensed can weight – returned can weight.
- **BMI (kg/m²)** = (weight in kg)/[(height in cm/100)²]. Day 1 height will be used for BMI derivation upto Week 24. For visits including week 24 through week 36, week 24 height

will be used to derive BMI. Week 52 BMI is derived using the height and weight collected at the same visit. This derivation is applied since height is not collected at all visits.

- **BMI Categories:**

- Underweight: $BMI < 18.5$
- Normal: $18.5 \leq BMI \leq 24.9$
- Overweight: $25.0 \leq BMI \leq 29.9$
- Obese: $BMI \geq 30.0$

- **WI-NRS 4-point reduction** = achievement of a 4-point reduction in WI-NRS pruritus score post-baseline compared to baseline, calculated only for subjects with a pruritus score of ≥ 4 at baseline.
- **Itch-free state** = achievement of in WI-NRS of 0 or 1.

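### The SAP 7.6 treatment-duration rows jump from 32 to 54 weeks, so 52-week completers are not counted as such from OLE baseline; Days on IP, read literally, also leaves out subjects who stop on confirmed clearance

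*SAP*

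**What the plan says.** SAP 7.6 tabulates subjects by treatment duration at ≥1 day, ≥8 and ≥12 weeks, then "≥ 24 weeks, ≥ 32 weeks, ≥ 54 weeks, and ≥ 62 weeks". Exposure is shown from both the primary and the OLE baseline. SAP 6.1.7 computes treatment duration in weeks as last application date minus first, plus 1, divided by 7.

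Dosing is once daily for at most 52 weeks (SAP 3.1) and in the evening (Protocol 5.6.3). The final visit is Day 365 with a 7-day window either side (Protocol 1.3 and 6.3). SAP 8 notes that the two baselines coincide for prior-vehicle and de novo subjects.

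Days on IP (SAP 6.1.7) uses the same first-to-last span, but then leaves out of the calculation those subjects who stop because the investigator has confirmed clearance. The nearby definition of expected applications removes time instead: "Excluding treatment-free interval time". Protocol 5.6.3 has subjects stop when the investigator finds them clear and restart when the disease returns. For subjects who entered after a break (Group 3), SAP 7.6 adds: "The gap between completing study ARQ-151-203 and enrolling into this study will not be included in the above definition". The definition meant there is Days on IP.

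**The concern.** The only objective is long-term safety over 52 weeks (Protocol 4.1, SAP 2.1.1). The sample size has no power or precision basis; it rests on long-term safety and, together with other studies, on exposure goals (SAP 3.2). The number of subjects treated for roughly the planned length is therefore a central figure in the exposure table. With no row between 32 and 54 weeks, that number merges with everyone who stopped after week 32.

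The Days on IP sentence raises a different problem. Taken literally, it removes responders who did what the protocol told them to do, and leaves a summary for a subset selected on response.

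**Working it through.** **Reproducing the plan's own days.** Week 52 from OLE baseline: 7 × 52 + 1 = Day 365 (SAP Table 3). From primary baseline for prior-roflumilast subjects: 365 + 56 = Day 421 (SAP Table 2). Both agree with the SAP.

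**In-window completer, OLE baseline.** The visit falls on Day 358 to 372. The last dose is either the evening before or on the visit day.

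| Visit day | Days, last dose the evening before | Days, last dose on visit day | Weeks |
|---|---|---|---|
| 358 | 357 | 358 | 51.0 or 51.1 |
| 365 | 364 | 365 | 52.0 or 52.1 |
| 372 | 371 | 372 | 53.0 or 53.1 |

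The ≥54 row needs 54 × 7 = 378 days. The shortfall is 378 − 372 = 6 to 378 − 357 = 21 days. The highest row reached is ≥32 (32 × 7 = 224 days) in every case. Only a completer seen late, outside the window, could enter ≥54.

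**Primary baseline.** Prior-vehicle and de novo subjects have the same figures as above. For prior-roflumilast subjects, assuming 56 parent-study days as Table 2 implies, the range is 56 + 357 = 413 to 56 + 372 = 428 days, or 59.0 to 61.1 weeks. They pass ≥54.

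**Where to put the row.** A strict ≥52 weeks is 364 days. With the last dose the evening before, visits on Days 365 to 372 qualify (8 of 15 in-window days) and Days 358 to 364 do not (7 of 15). A row at ≥51 weeks, 51 × 7 = 357 days, takes in every in-window completer who doses to the end.

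**Days on IP, worked example.** A subject doses on Days 1 to 84, is off drug on confirmed clearance, and doses again on Days 253 to 364.
- Doses given: 84 + 112 = 196.
- First-to-last span: 364 days (52.0 weeks).
- Days on IP read literally: the subject is not in the calculation.
- Subtracting off-drug days as next dose date minus last dose date minus 1: 253 − 84 − 1 = 168, and 364 − 168 = 196, which matches the doses.
- The SAP's treatment-free interval would not serve for this subtraction, because it runs from "the date of stop treatment due to attainment of score of IGA of 0 +1". It gives 253 − 85 + 1 = 169 or 253 − 84 + 1 = 170, depending on which day counts as the stop date, and so 195 or 194 rather than 196.

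**The case against.** The strongest reply is that other outputs already show who reached a year. Disposition (SAP 7.1, Protocol 7.1.6) counts completers and discontinuations, and is the nearest planned figure. By-visit tables give a Week 52 n: "The denominator for by-visit displays will be the number of subjects in the relevant study population with non-missing data at each visit". SAP 7.6 also promises that "Study duration will be summarized from primary and OLE baseline", summarises the number of applications, and sets the shorter-schedule subjects apart: "Similar exposure and compliance information will be summarized for subjects who completed or discontinued study before protocol amendment 1".

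These help, but only in part. Disposition and Week 52 n measure completion or follow-up, not dosing. A subject who doses on Days 1 to 252, is confirmed clear at Day 253 and stays off drug is a completer with 252 / 7 = 36.0 weeks of treatment. Early-termination data can count as Week 52 when no scheduled value exists and "the early termination or unscheduled/repeated measurement falls within the analysis visit windows"; in Table 3 that window opens at Day 310 (310 / 7 = 44.3 weeks). Study duration has no definition in SAP 6.1.7 and no cut-offs. The descriptive summary of applications gives no count at a threshold. The separate summary for subjects who left before Amendment 1 pools completers with discontinuations.

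Second, Days on IP may well have been meant to remove time, as the expected-applications definition does. That is plausible. The sentence nevertheless says subjects, so it needs rewording whatever was intended.

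Third, first-to-last treatment duration is an explicit and defensible measure of elapsed time. That stands, and no fault is claimed in the formula itself. The one open question is whether it includes the Group 3 gap, since the SAP excludes that gap only from Days on IP and from the visit windows.

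**Conclusion.** The point holds and is minor. From OLE baseline no in-window completer reaches ≥54 weeks, and the treatment-duration table gives no count of subjects treated for about 52 weeks in this study. This assumes dosing to the end, a visit within ±7 days, and a last dose on the visit day or the evening before. The effect of the Days on IP wording cannot be sized, because the documents do not say how many subjects stop on clearance.

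A reader might infer more than the documents support:
- **That the plan counts nobody with a year of exposure.** Prior-roflumilast rollovers are counted in ≥54 from primary baseline.
- **That the ≥62 row is wrong.** Whether it can be reached depends on the parent study's visit window, which is not given.
- **That the exposure goals are missed.** They are tied to this study in combination with others, and neither document states a duration or a number.
- **That safety conclusions are compromised.** Dose dates are collected and the TEAE and SAE analyses do not use these rows. A count could still be made later, but under SAP 1 it would have to be identified as unplanned.

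**What to change.** 1. In SAP 7.6, keep the existing rows and add one near 52 weeks with a stated visit-window allowance, for example ≥51 weeks (357 days). A row near 60 weeks from primary baseline is optional and needs the same allowance: a strict 420 days, less 56 parent-study days, again requires 364 days in this study.
2. In SAP 6.1.7, define Days on IP for all subjects as last minus first dose date plus 1, minus off-drug days in confirmed-clear intervals (next dose date minus last dose date minus 1), and minus the Group 3 gap. Off-drug time after the last dose is already outside the span.
3. State that Treatment Duration also excludes the Group 3 gap.
4. As a clerical matter, reconcile the parent-study number in the SAP 7.6 gap sentence with ARQ-154-203, which is used for Group 3 elsewhere.

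The cost is SAP wording and one re-programmed table, with no new data. Days on IP will come out somewhat lower than elapsed treatment duration, which the table should note.
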